### Research Questions and Hypotheses:

*Specific Aim 1: To determine the impact of service dogs and determine who benefits the most.*

**Hypothesis 1A:** Individuals partnered with SDs will have greater improved mental health over time (Primary outcome will be the PCL checklist. Secondary mental health will be quantified by scores on depression and alcohol use).

**Hypothesis 1B:** Individuals partnered with SDs will have improvements over time in secondary factors of physical, psychosocial, and socioeconomic variables. The secondary factors are defined as follows: 1) physical factors: co-morbidities, medication use, sleep 2) psychosocial factors: community participation, quality of life and 3) socioeconomic factors: demographic and health care utilization and out-of-pocket health care expenses.

*Specific Aim 2: To determine costs associated with total health care utilization and mental health care utilization among Veterans with mental health disorders needs and service or therapy dogs.*

**Hypotheses 2A:** Individuals partnered with SDs will have decreased mental health care utilization over time.

**Hypotheses 2B:** Individuals partnered with SDs will have decreased total health care utilization over time.

*Specific Aim 3: To determine recommendations for providing service dogs to Veterans.*

Develop a strategic plan to provide service dogs to Veterans. A consensus meeting will be planned and will include all investigators of the project along with key individuals from funding agency to discuss findings of study.

*Secondary Aim:* To compare study findings to another VA funded study that is providing dogs as pets to Veterans with PTSD. Both studies are using similar measures to assess mental and psychosocial factors. Data will be compared across groups (SD to dog as a pet) to determine if the highly trained dogs help the Veteran more than having a dog as a pet.

*Projected Time Table*

Training of SDs is time intensive and expensive, with limited numbers of dogs who actually graduate. We will work with vendors to obtain the dogs, but recognize that there may be a significant waiting period prior to pairing. To demonstrate maximum treatment benefits, the data collection phase of this three-year study will be conducted for a minimum 18 months (maximum of 24 months for early enrollees) as we feel the acclimation period for the human-animal bond is longer than 18 months. This allows sufficient time for statistical analyses.

*Timeline*

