### **Research Design and Methods**

#### *Design*

This 3-year, mixed methods modified, non-randomized trial will follow individuals for two years. Due to the inability to recruit veterans interested in participating in a control (no dog) group, this group has been eliminated going forward with the study. The study will examine the influence of SDs by assessing the longitudinal change in mental health assessment over time among veterans who have PTSD. The group will consist of individuals partnered with SDs. Following initial screening for inclusion criteria, including criteria set by dog vendors, subjects who are eligible will receive a SD. This study will measure changes over time in the primary outcome of mental health. Additional outcomes in psychosocial health and healthcare utilization will be included. Recruits successfully completing the screening process will be placed on a vendor's waiting list to receive a SD upon the dog's completion of training. Recruits who do not meet all criteria, including vendor criteria, will be ineligible to participate..

Data will be collected at baseline and at 3, 6, 9, 12, 18 and 24 months for individuals with service dogs. For those awaiting service dogs, repeated assessments will occur every 3 months until obtaining a SD. Once baseline data has been collected for 24 months, assessments will occur every 6 months until the Veteran is paired with a SD. Baseline data will include detailed information on the characteristics of the participants, their mental health, psychosocial well-being, socioeconomic and healthcare utilization characteristics. As we want to obtain information regarding the changes in health and wellbeing over time, a prospective study will permit this type of comparison.

*Sample:* The study will use a convenience sample of VHA patients who are currently in treatment for PTSD. We have chosen to use these criteria as a safety measure for the veteran and the dogs. At this time, there are currently 600 veterans receiving care at James A. Haley VAMC for PTSD, with an estimated 25 new veterans seen in the clinic per week. We are confident that an adequate number of Veterans will be recruited for the study. We will monitor recruitment and retention numbers on a monthly basis. The use of additional VA hospitals as a potential source for recruitment is the contingency plan should we be unable to meet enrollment numbers.

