**Analysis:** The distribution of each variable will be examined for outliers to determine if transformations (to normalize data) are necessary. Initially, means  $\pm$  SD, and medians, will be calculated for all continuous measures (e.g., age, psychological scales). Frequencies and percent will be determined for categorical variables (e.g., gender, race, etc.). Variables considered ‘confounders’ (demographic and dog predisposition questionnaires) would be compared across time for the relevant hypotheses. Categorical variables (e.g., gender, race, disability) will be compared across groups using chi-square. Continuous variables (years of disability, dog predisposition scores) will be compared using ANOVA. Baseline differences will be noted and controlled for in additional analyses. A significance level of ( $\alpha < 0.05$ ) will be used for all analyses. All data will be managed as intent to treat.

Statistical Analyses are presented below by hypothesis:

**Hypothesis 1A:** *Individuals partnered with SDs will have greater improved mental health over time.* Baseline data will be examined. Observed significant differences will be used as covariates in modeling, they will be controlled in subsequent analysis. For this hypothesis, a linear repeated measures mixed model will be used to determine changes over time between groups. PCL-checklist scores will be considered the dependent variable. Baseline PCL-C scores will be introduced in all models as covariates. These scores are continuous. The use of mixed models allows for control of covariance data expected in clustered and repeatedly sampled data, and missing data. We expect the SD group to have greater functional independence and community participation at the end of the study.

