We expect some individuals to benefit more than others. We hypothesize that individuals with greater limitations will have the most improvement when provided with an SD. Consequently, we will conduct a sub-analysis of the SD group. We acknowledge this is an exploratory analysis and the power is limited. The hypothesis we will test is individuals who score lower in psychosocial factors (e.g. community participation) at baseline will show greater improvements in those characteristic than individuals who scored higher. Therefore we will use the subcomponents scores of continuous measures and dichotomize them at a clinically meaningful point (e.g.,  $\geq 80 \geq 75^{\text{th}}$  percentile) at the baseline measure. All individuals will be put into one of two groups based on this cutpoint. Repeated measures analyses will be completed on all continuous variables with the between factor being the two groups and the within measure equaling variables of physical, psychosocial and economic characteristics.

In addition, we will conduct an exploratory analysis to determine whether relationships exist between group status (SD vs. control), demographic variables (age, gender, living arrangements, marital status, etc.) and the outcomes of interest – mental health (, PCL-C) and psychosocial factors (e.g. community participation). Categorical demographic variables will be analyzed using a chi-square for variables that are dichotomous, and one-way ANOVAs will be used for continuous variables that have multiple categories. Continuous demographic variables (e.g., age) will be compared to the outcomes using correlations: Pearson for normally distributed variables and Spearman rho for not-normally distributed variables. Sub-analysis will examine the relationship between the outcomes of interest and the physical, psychosocial and economic variables. Correlation analysis will be used to determine significant relationships. Two separate multiple regression models will be developed using any variables significant at a  $p$ -value  $< 0.10$  in the univariate analysis. The outcomes will be from the 18-month visit, whereas the predictor variables will be those recorded at baseline. These analyses will be used to describe those characteristics of Veteran's most likely to benefit from obtaining a SD compared to control subjects.

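### With the control group removed, the exploratory 18-month regressions estimate prognosis and cannot show which Veterans benefit from a service dog

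*Combined protocol and SAP*

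**What the plan says.** The analysis in question comes after the Hypothesis 1B text in Data Management and Statistical Analysis, in the paragraph on demographic variables and outcomes. It is called exploratory and is meant to "determine whether relationships exist between group status (SD vs. control), demographic variables" and the outcomes, which are the PCL-C and psychosocial factors such as community participation. The rule is: "Two separate multiple regression models will be developed using any variables significant at a" p-value below 0.10 in the univariate step. Then: "The outcomes will be from the 18-month visit, whereas the predictor variables will be those recorded at baseline". The stated use is: "These analyses will be used to describe those characteristics of Veteran's most likely to benefit from obtaining a SD compared to control subjects". A 0.05 significance level "will be used for all analyses".

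The Design section says of the no-dog control group that "this group has been eliminated going forward with the study", and of what remains: "The group will consist of individuals partnered with SDs". Specific Aim 1 reads: "To determine the impact of service dogs and determine who benefits the most".

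Two other planned analyses bear on the same question: predictors of success after 18 months (under Hypothesis 1B), and a repeated-measures sub-analysis of the dog group split by baseline score. Under Hypothesis 1A, the plan also puts the baseline PCL-C score into all models.

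**The concern.** Benefit is a contrast between a Veteran's outcome with a dog and the outcome that Veteran would have had without one. Knowing who benefits more requires knowing how that contrast varies with a trait. These models use only baseline traits and an 18-month level, in people who all have dogs.

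A trait that goes with worse PTSD symptoms at enrolment will tend to go with worse symptoms at 18 months, because scores persist. The regression would find that trait with or without dogs. Read as the plan intends, markers of severity such as depression, poor sleep or low participation could be reported as marks of benefit, or of lack of it.

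**Working it through.** **1. The plan's own figure.** No operating characteristic is given for these regressions. The only figure on effect modification is in the Sample text: approximately 100% power for a dog-group-by-covariate interaction. It cannot be rebuilt, because group sizes and error SD are not given, and one effect size (5.54) is paired with two SDs (0.47 and 0.8). That interaction also needs two groups.

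**2. What the coefficient estimates.** Let T be a baseline trait and D indicate having a dog:

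Y18 = a + b·T + D·(c + g·T) + error.

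Differential benefit is g. If D = 1 for everyone, the coefficient on T is b + g, and the two parts cannot be separated. If the dog does nothing (c = g = 0), the coefficient is b, which is pure prognosis. This needs no assumed numbers.

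**3. Inputs for the size.**
- N = 220 − 33 = 187, from the Sample text's 15% dropout. The same text expects 200 completers.
- First-order autocorrelation 0.80 (Sample text). Baseline to month 18 is five visit steps, so r = 0.80^5 = 0.328.
- Screen at p<0.10, then multiple regression at 0.05, taken as two-sided.
- Assumed: four baseline scales correlated 0.3-0.5 with baseline PCL, plus 0 to 10 unrelated traits. As an alternative to AR(1), a stable severity component with reliability 0.6.

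**4. Chance of declaring at least one trait when the dog effect is zero (N = 187).**

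| Structure of scores | Baseline PCL not entered | Baseline PCL entered |
|---|---|---|
| AR(1), 0.80 | 61-84% | 9-45% |
| Stable severity, reliability 0.6 | 100% | 92% to over 99% |

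The ranges cover separate simulation runs and 0 to 10 unrelated traits.

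Further checks at N = 187-200, with baseline-to-18-month correlation from 0.26 (0.80^6) to 0.80:
- A trait correlated 0.3 with baseline PCL, with no other link to outcome, passes the screen in 27-96% of runs. With baseline PCL entered, it is significant in only 4-7%.
- A trait with its own partial prognostic correlation of 0.2 is still significant after baseline adjustment in 78-82%.
- With ten traits wholly unrelated to outcome, at least one passes the screen with probability 1 − 0.90^10 = 65%, and the final model has one below 0.05 in 38-43%.
- If 0.80 per visit also applies to community participation, its baseline value predicts its 18-month value with probability Φ(atanh(0.328)·√184 − 1.96) = Φ(4.62 − 1.96) = 99.6%.

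**5. Does a before/after interaction rescue the question?** The plan assesses waiting Veterans every 3 months, so one could test trait by phase (waiting versus with dog). With zero dog effect, N = 187, the trait measured at enrolment, and the mean of six post-pairing visits compared with the mean of two waiting visits, the false-positive rates are:
- pure AR(1) 0.80: about 50-92% for trait correlations 0.3-0.5;
- stable component (variance 0.4 or 0.6) plus AR(1) remainder: 23-74%;
- the trait being the outcome scale itself, with the enrolment visit dropped: 99-100% in these AR(1) settings;
- stable component plus remainder independent between visits: about 5%.

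Waiting visits lie nearer to enrolment than post-pairing visits do, so regression to the mean looks like a trait-dependent dog effect.

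**6. What would work.** A trait-by-group term with two equal groups rejects 4-6% of the time under no effect, even for a prognostic trait. At 65 per group it has about 40% power for an interaction of 0.3 residual SD per trait SD, and 80% power at about 0.49. With one group it cannot be estimated.

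**The case against.** **The analysis is labelled exploratory.** It is, and that lowers the weight of the finding. The label excuses imprecision, but it does not turn a prognostic coefficient into a benefit estimate.

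**The paragraph lists group status, dog versus control.** With one group that variable is constant. The Design wording leaves open whether any controls were enrolled earlier, but no trait-by-group term is named in this paragraph in any case.

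**Baseline PCL-C goes into all models.** The sentence sits under Hypothesis 1A, so its reach is arguable. If it applies, it helps: under the plan's AR(1) the rate falls to 9-45%, and much of what remains comes from testing several traits. It does not help much if severity has a stable part that one noisy baseline measures imperfectly, and it does not supply the missing contrast.

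**Stronger readings that the documents do not support.** A reader might infer that false benefit traits are certain. The rates depend on trait correlations, reliability and a number of traits that the documents do not give. A reader might also infer that these models alone answer the who-benefits part of Aim 1. The sub-analysis by baseline score and the predictors-of-success model bear on it too. Nor does the plan tie the Aim 3 recommendations to these regressions; it describes a consensus meeting on the study's findings.

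**Conclusion.** The concern stands on the design: an 18-month level regressed on baseline traits, in Veterans who all have dogs, estimates prognosis. The stated conclusion about benefit relative to controls cannot be drawn from it.

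The size is conditional. With no dog effect, the chance of naming at least one trait runs from about 9% (AR(1) 0.80, baseline PCL entered, few traits) to near 100% (stable severity, reliability 0.6). The documents fix only the sample size, the autocorrelation and the two p-value thresholds; the rest is assumed. Using 200 completers instead of 187 does not change the conclusion.

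This is a secondary matter, since it leaves the primary PCL analysis untouched. It does govern what the trial may say from these models about who benefits.

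**What to change.** In the exploratory paragraph of the statistical analysis section:

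1. Enter the baseline value of the outcome in each regression (baseline PCL for PCL, baseline participation for participation).
2. Label the models *predictors of 18-month status among Veterans with a service dog*.
3. Delete the closing claim about Veterans most likely to benefit compared with control subjects.
4. Reconcile the dog-versus-control wording here, and in the repeated logistic regression under Hypothesis 1B, with the Design section.

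Do not substitute a trait-by-phase interaction as the test of benefit. If it is explored, model trait by time since enrolment as well, and report the result as non-randomised and descriptive.

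The cost is a few sentences and minor programming, with no new data. The downside is that the trial can no longer claim from these models who benefits from a dog.

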#### *Measurements: Outcomes and Independent Predictors*

The outcomes to be measured by this study will be grouped into four categories: mental health, physical, psychosocial and socioeconomic/healthcare utilization. Table 2 shows an outline of the study outcomes, predictor variables, and possible confounders to be obtained from all participants.

Table 2: Measurements

	Constructs	Measures	Burden
Mental Outcomes	PCL -S	PTSD diagnosis/symptom severity	5 minutes
	Depression	PHQ-9	5 minutes
	Alcohol use	AUDIT-C	5 minutes Time point: baseline, final
Physical Factors	Co-morbidities	Medical record,	None to subject**

	Constructs	Measures	Burden
	Medication	Type, class, dose	None to subject **
	Sleep	Pittsburgh Sleep Index and PSQI Amendment for PTSD	10 minutes
Psychosocial Factors	Health-related Quality of Life	SF12	10 minutes
	Community participation	Community Integration Questionnaire	10 minutes
	Demographic	Age, gender, race/ethnicity, marital status	5 minutes
Service Dog	Satisfaction Tasks	Behavior, Level of satisfaction with the performance of service dog and what tasks are completed	10 minutes Follow up visits 1, 2, 3 and thereafter; only after pairing
Economics	Socioeconomic factors	Employment, hours worked, years of education, health insurance, income	5 minutes
	Healthcare utilization	Number of visits to healthcare in previous 3 month time period, for both mental health and general health care visits	
	Healthcare costs	Out of pocket expenses, self-report of outside healthcare	10 minutes

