### Other Forms

Form	Purpose	When Completed	Who Completes
Home environment checklist	Checklist to assess home environment prior to dog placement	Pre-pairing home visit	Study Team Dog Trainer
Dog Care Test	Test knowledge of dog care and responsibility	After completion of Dog Care Course	Veteran
Service Dog Post Pairing Evaluation	Assess pairing and identify potential health or behavior problems in dogs	One week post pairing, months 1, 2, 3, 6, 9, 12, 18, 24	Study Team Dog Trainer at home visit
Veterinarian Checklist	Assess dog's health	Once per year	Veterinarian caring for each dog
Veteran Guide for Veterinary Care	Provides information to Veteran about maintain dog's health	Provided when Dog Care Course is completed	Information provided to Veterans
Home visit information sheet	Provides information to Veterans about how and why the home visit is done	Provided after IC, prior to home visit	Information provided to Veterans

Service Dog Questions	Veteran's subjective report about the dog's behavior and Veteran's satisfaction with the dog	Months 3, 6, 9, 12, 18, 24	Study team member present at home visit
-----------------------	--	----------------------------	---

Unless otherwise noted, all measures are completed at all visits.

\*\*Data for these items will be abstracted from medical record

Mental Outcomes: Outcomes for the main hypotheses will be measured with the following measure using the PTSD Checklist (PCL). PTSD Checklist is a 17-item self-report measure of the 17 DSM-IV symptoms of PTSD. Respondents rate how much they were “bothered by that problem in the past month”. Items are rated on a 5-point scale ranging from 1 (“not at all”) to 5 (“extremely”). The PCL can be scored in several different ways. A total score (range 17-85) can be obtained by summing the scores from each of the 17 items. Although the CAPS was used initially for the study, it was decided by the research team with input from the funding agency that diagnosis of PTSD will be confirmed by referring clinician and eliminate stress of completing the interview for the veteran. For some of the veterans that are enrolled in the study, CAPS is available in their medical record. If it is available, we will abstract the information to further confirm the diagnosis.

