Power analysis for Hypotheses 1: All power analyses were completed with PASS 6.0^81. Given a minimum sample size of 65 (per group), and an alpha of 0.05, we have over 80 percent power to detect differences in socioeconomic characteristics. This power analysis is based on changes in mean and SD (PCL-C) from prior published studies. This power analysis allows for the addition of three covariates to be added to the model.

***Hypothesis 2A:*** *Individuals partnered with SDs will have decreased mental health care utilization, over time.* We expect the SD group to experience diminished healthcare utilization over time. A within subject repeated measures will be completed to determine changes over time for healthcare utilization.

***Hypothesis 2B:*** *Individuals partnered with SDs will have decreased overall health care utilization, over time.* We expect the SD group to experience diminished healthcare utilization over time. A within subject repeated measures will be completed to determine changes over time for healthcare utilization.

*Exploratory Aim:* We will compare our findings to data collected in similar study entitled, “A Study of Dog Adoption in Veterans with Posttraumatic Stress Disorder” which is being conducted by [name] at the South Texas Veterans Healthcare System in San Antonio, TX. This is a 2-year pilot study examining the use of shelter dog adoption as a supplement to standard care in reducing PTSD symptoms in Veterans. 24 veterans will be randomized to adopt a dog from the Humane Society while another 24 (control group) will be randomized to a wait-list and be eligible to adopt a dog after 3 months. Outcome measures will be assessed at baseline and at 3 intervals (1, 3, and 6 months post-randomization) for Veterans in the experimental group and 4 intervals (1, 3, 4, and 6 months) for those in the control group. Data collection will be in the form of face-to-face interview as well as self administered paper forms. CPRS records will be reviewed for changes in mental health treatments, medications, diagnoses, and other health related variables. Analysis will be completed which will examine similar measures (e.g. PCL checklist, depression, community integration) across our Veterans who received service dogs at three time points (baseline, three and six months) to their Veterans who received dogs as pets. As this is an exploratory analysis, power analysis was not completed.

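### The over-80% power is claimed for socioeconomic characteristics but rests on PCL-C inputs and a two-group design, so it has no stated basis for the outcome it names

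*Combined protocol and SAP*

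**What the plan says.** The paragraph on power for Hypotheses 1 (Data Management and Statistical Analysis) opens with "Given a minimum sample size of 65 (per group), and an alpha of 0.05" and continues "we have over 80 percent power to detect differences in socioeconomic characteristics". The next sentence gives the source of the inputs: "This power analysis is based on changes in mean and SD (PCL-C) from prior published studies". It ends with "This power analysis allows for the addition of three covariates to be added to the model". The mean change and the SD are not printed.

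Elsewhere the plan keeps the two outcomes apart. In Research Questions and Hypotheses, Hypothesis 1A says "Primary outcome will be the PCL checklist". The Measurements text describes the PCL as a symptom scale: "A total score (range 17-85) can be obtained by summing the scores from each of the 17 items". Hypothesis 1B defines "socioeconomic factors: demographic and health care utilization and out-of-pocket health care expenses". Table 2 lists the socioeconomic items as "Employment, hours worked, years of education, health insurance, income", with visit counts and out-of-pocket costs on separate rows under the same economics block.

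The Design section states that the control group was dropped because veterans could not be recruited to it, leaving one group, all partnered with service dogs.

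**The concern.** Power belongs to a particular outcome, because it depends on the change expected in that outcome and on its variability. An effect and an SD taken from a PTSD symptom score do not give power for income, employment, visit counts or expenses. Some of these are categorical or counts, and the Hypothesis 1B analysis itself provides GEE for categorical outcomes. One mean-and-SD calculation could not cover the whole set.

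Two things are at stake. First, a secondary domain is credited with power that was not calculated for it, while the paragraph does not name the PCL as the powered outcome. Second, the Hypothesis 1B analysis text treats health care utilization as the socioeconomic variable, and utilization is also the outcome of Hypotheses 2A and 2B, which have no power statement of their own. A reader could take the 80% as covering those too, and could then read a null utilization or cost result as adequately powered.

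**Working it through.** **Inputs from the plan.** Minimum 65 per group; alpha 0.05 with sidedness not stated; power over 80%; three covariates; PCL-C change and SD from published studies, values not given. From the Sample paragraphs: up to 220 enrolled, 15% drop-out (33), 200 expected to complete.

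**Reproducing the 80%.** This cannot be done directly, because the change and SD are missing. The standardised effect that the claim implies can be back-solved (normal approximation, z(0.975) = 1.96, z(0.80) = 0.84, sum 2.80):

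- Two groups of 65: d = 2.80 × sqrt(2/65) = 0.49 SD. The t-based value is 0.495, with or without 3 degrees of freedom removed for covariates. One-sided, it is 0.44.
- One group of 65, within-subject change: d = 2.80 / sqrt(65) = 0.35 SD of the change score (t-based 0.353).

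So over 80% is arithmetically possible for the PCL-C if the published studies showed about 0.49 SD or more between groups.

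**Looking for socioeconomic inputs.** The plan states no assumed change, SD, rate or dispersion for any socioeconomic or utilization variable. The background and preliminary studies mention some costs and assistance hours in people with other disabilities, but give no SDs for them, and the power paragraph does not use them. The other power statement, in the Sample section, claims about 100% for dog group status, covariates and interactions, and names no socioeconomic outcome.

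**Power over an assumed range.** Two-sided 0.05, normal approximation. One group: power = Φ(d·sqrt(n) − 1.96), plus a negligible lower tail. Two groups: replace sqrt(n) by sqrt(n/2). The effect sizes are assumptions, since the plan gives none.

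| Assumed effect (SD) | One group, n=65 | Two groups, 65 each |
|---|---|---|
| 0.1 | 13% | 8% |
| 0.2 | 36% | 21% |
| 0.3 | 68% | 40% |
| 0.4 | 90% | 63% |

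Worked example, one group at 0.3 SD: 0.3 × sqrt(65) = 2.42; 2.42 − 1.96 = 0.46; Φ(0.46) = 0.68. In two groups, 0.5 SD gives 81%.

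**Detectable change at the planned size.** The Sample paragraphs support two numbers: 220 − 33 = 187, and the stated 200 completers. One group, 80% power: 2.80 / sqrt(187) = 0.205 and 2.80 / sqrt(200) = 0.198, so about 0.20 to 0.21 SD of change.

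**The case against.** The strongest reply is that the noun is a slip. The heading covers all of Hypotheses 1, and the only inputs cited are for the PCL-C, so the 80% was probably meant for the PCL. That is plausible. The sentence would still name the wrong outcome, and Hypothesis 1B would then have no power basis at all, so a correction is needed either way.

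A reader might infer more: that the study lacks 80% power for socioeconomic outcomes. The documents do not support that. The figure cannot be reproduced or refuted without its inputs, and the table falls on both sides of 80% depending on an effect the plan never states. With 200 analysed, even 0.2 SD gives about 81% (0.2 × sqrt(200) = 2.83; Φ(0.87) = 0.81).

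A reader might also take 65 as contradicting the recruitment target. It does not: 65 is given as a minimum, and a larger sample raises power. What does not fit is the per-group wording after the control group was removed.

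Two further cautions stand. The calculations above are for a single change score, whereas the plan uses repeated-measures mixed models or GEE with covariates, so the percentages are illustrative. These are also secondary outcomes, and no decision rule in the plan depends on this figure. The misreading of a null result is therefore a risk of interpretation, not something the plan commits to.

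**Conclusion.** The point holds as one of attribution. The plan attaches a power figure to socioeconomic characteristics, derives it from the PCL-C, and gives no planning inputs for any socioeconomic variable. The figure is also framed for two groups in what is now a single-group study. Its size for socioeconomic outcomes is unknown: at n=65 in one group it runs from about 13% to 90% as the assumed change goes from 0.1 to 0.4 SD, and it passes 80% only from about 0.35 SD. Those values assume two-sided alpha 0.05, effects in SDs of the change score, and a normal approximation. The supportable conclusion is that the stated power is unsupported for the outcome named, not that it is false.

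**What to change.** 1. Delete the power claim for socioeconomic characteristics, or replace it with a calculation for a named socioeconomic variable using that variable's own expected change and variability.
2. Name the PCL as the outcome that the present calculation describes, and give the mean change, the SD (of change or of baseline) and the sidedness of alpha.
3. Redo the PCL figure for the single-group, within-subject design. Moving the existing 80% across to PCL change would keep a calculation made for 65 per group.
4. For Hypothesis 1B outcomes, say that no power was planned and give the detectable standardised change at the number expected to be analysed: about 0.20 SD at 200 or 0.21 SD at 187. First reconcile the 15% drop-out from 220 with the 200 expected completers.

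The cost is a few sentences, one recalculation and a less favourable power statement for the secondary outcomes. No visit, measure or recruitment target changes.
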